6.2 IMPORTANT PROTOCOL DEVIATIONS

No per protocol set (PPS) analysis will be performed, hence, no patient will be excluded from the analyses (with the exception of patients not providing informed consent). However, patients with potentially important protocol deviations (iPDs) will be documented to give an indication of the level of adherence to the protocol, refer to [Table 6.2: 1](#). Note this is a working list and may not be finalised until the final Medical Quality Review Meeting (MQRM), Database Lock Meeting (DBLM) and Report Planning Meeting (RPM) have taken place prior to the database lock of the primary PFS analysis.

A frequency table of the above iPDs will be produced. In addition, a frequency table of all COVID-19 related non-important and important PDs will be produced.

Table 6.2: 1 Handling of iPDs

[figure not shown]
iPD code	iPD Category & Brief Description	Analysis Set Excluded from
A1	Diagnosis of trial disease questionable	None
A2	Prohibited baseline condition, diagnosis or treatment	None
A3	Laboratory result indicating inadequate organ function at screening	None
A4	Adequate archival tumour tissue not available	None
B1	Informed consent not available/not done	All
B2	Informed consent too late	None
B3	Age limit for patient inclusion not adhered to	None
C1	Time window violation for procedures performed at screening	None
C2	Trial medication not given according to protocol	None
C3	Infusion time for the investigational treatment outside of CTP specific boundaries	None
C4	Randomisation not followed	None
D1	Prohibited treatment during trial conduct phase	None
E1	Imaging assessments not done according to CTP instructions	None
F1	Other protocol violations affecting patient rights or safety	None

6.3 PATIENT SETS ANALYSED

The following patient sets are defined:

- **Enrolled set:**
This patient set includes all patients who have given informed consent. The enrolled set will be used for patient disposition summaries.
- **Randomised set (RS):**
This patient set includes all randomised patients, regardless of whether they have received treatment or not. The RS will be used for demographic and baseline characteristic summaries and the evaluation of primary, secondary and further endpoints.

- Treated set (TS):
This patient set includes all patients who are documented to have received and taken at least one dose of any study medication. The TS will be used for the evaluation of safety.
- PK parameter analysis set (PKS):
This patient set includes all patients in the TS who have at least one valid drug plasma concentration available that was not excluded because of protocol deviations affecting PK evaluation.

6.5 POOLING OF CENTRES

This section is not applicable because centre is not included in the statistical model.

6.6 HANDLING OF MISSING DATA AND OUTLIERS

In general, missing data will not be imputed, unless required for the following analyses and definitions. Then the rules as described below apply.

For TTE endpoints, patients who are event-free but have dropped out of the trial prematurely or are not evaluable for other reasons will be censored according to the rules given in [Sections 5.1, 5.2 and 5.3](#).

The BPI-SF pain interference aggregated score will only be calculated if 4 or more of the 7 individual item scores have been completed.

Missing or incomplete dates that affect the evaluation of endpoints will be imputed utilising a worst-case approach, which will be applied on a case-by-case basis (depending on the affected endpoint) and documented appropriately prior to database lock and unblinding.

For the purposes of potential PFS censoring incomplete start dates of subsequent anti-cancer therapy will be imputed. The earliest possible date will be assumed, if this results in a start date prior to the stop date of study treatment this will be defaulted to study treatment stop date + 1 day.

Missing or incomplete adverse event (AE) dates will be imputed according to BI standards [\(2\)](#).

For the calculation of time to first diagnosis, if the date of diagnosis is incomplete the 1st will be used for a missing day and January for a missing month.

In general, actual patient data as reported in the eCRF will be used for analyses. If the data relating to the assignment of stratification factors are missing in the eCRF then the values entered into the Interactive Response Technology (IRT) system will be used instead (note these entries are automatically transferred to the eCRF).

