For patients in FU-PD (i) (who came off trial treatment before the end of Cycle 20) imaging every 8 weeks (56 days) and (ii) (who received treatment beyond cycle 20) every 12 weeks (84 days). Imaging procedures will be performed until progression or start of further anti-cancer therapy. For patients starting further anti-cancer therapy without objective progression, imaging should be performed prior to starting the new therapy if no image has been performed within the last 4 weeks. If patients continue treatment beyond progression, imaging must also be continued and sent to a central imaging CRO.

In the event of early discontinuation or an interruption/delay to treatment the tumour assessment schedule should not be changed.

- 11 Patients will be randomised after all SV procedures have been completed and eligibility is confirmed. Treatment must commence as soon as possible after randomisation, but within 7 days at the latest.
- 12 Xentuzumab/placebo will be dispensed weekly. Drug holidays of up to 14 calendar days will be allowed for xentuzumab/placebo as described in [Section 4.3.1](#). In case of drug holidays please also refer to footnote 14.
- 13 From Cycles 1 to 20 everolimus and exemestane will be dispensed at V1 of each cycle. After cycle 20 (week 80), dispensation will take place at V1 and V5 of each cycle.
- 14 A patient diary will be given to the patient for continuous use through the trial. It should be given to the patient at the start of each cycle. The diary collects information about medication taken at home and provides reminders about fasting bloods and urine samples. After one week on study medication, treatment compliance should be discussed with the patient, to ensure that the medication is being taken correctly (no compliance calculation has to be performed). Then at Visit 1 of each cycle and at EOT treatment compliance needs to be checked including compliance calculations.
- 15 Pharmacokinetic, ADA/nAb and cytokine sampling will take place as described in [Appendix 10.1](#). If a patient misses xentuzumab/placebo infusions due to drug holidays replacement samples for PK, ADAs, nAbs should be drawn at -0:05 timepoint, before the next infusion.
- 16 Biomarker blood sampling will take place at pre-dose at C1V1, C2V1. At C2V1 an additional sample will be taken 15 min. (±5 min.) after end of xentuzumab/placebo infusion as described in [Appendix 10.1](#).

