7.5 HANDLING OF MISSING DATA

In general missing efficacy data will not be imputed and all reasonable efforts will be taken during the study to obtain such data. Patients with unknown vital status, missing tumour imaging data and missing PRO assessments will be censored for time to event analyses as detailed below.

[Table 7.5: 1](#) describes how patients will be classified for the analysis of PFS. Sensitivity analyses will examine the effect of using alternative rules.

Table 7.5: 1 Derivation rules for PFS

Situation	Outcome	Date of outcome
No baseline radiological assessment		
Death on or before the second planned radiological assessment	Event	Date of death
Alive or death after second radiological assessment	Censored	Date of randomisation
Without post-baseline radiological assessments		
Vital status is unknown or known to be alive	Censored	Date of randomisation
Death prior or on the second planned radiological assessment	Event	Date of death
Death beyond the second planned radiological assessment	Censored	Date of randomisation
With baseline and post-baseline radiological assessments BUT no other anti-cancer therapy		

Table 7.5: 1 Derivation rules for PFS (cont'd)

Alive and not progressed, no more than one consecutively missed radiological assessments	Censored	Date of last radiological assessment
Alive and not progressed, two or more consecutively missed radiological assessments	Censored	Date of last radiological assessment prior to missed radiological assessments
Progressed, zero or one missed radiological assessment prior to progression	Event	Date of radiological assessment of progression
Progressed, but two or more consecutively missed radiological assessments prior to progression	Censored	Date of last radiological assessment prior to missed assessment
Death but no progression, zero or one missed radiological assessment prior to death	Event	Date of death
Death without progression, but two or more consecutively missed radiological assessments prior to death	Censored	Date of last radiological assessment prior to missed assessments
Initiation of subsequent anti-cancer therapy		
Subsequent anti-cancer therapy started before progression or death	Censored	Date of last radiological assessment before subsequent anti-cancer therapy
No baseline and/or post-baseline imaging and subsequent-anti cancer therapy started prior to a death	Censored	Date of randomisation

For endpoints related to OR and DC the rules defined above, where applicable, will be followed.

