Subsequent anti-cancer therapy started before the outcomes flagged with a '*' above	Censored	Date of last radiological assessment before subsequent anti-cancer therapy (or date of randomisation if none exist)

* For these outcomes if initiation of subsequent anti-cancer therapy occurred prior to the outcome date then the rule for the final row of table will be used instead

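### Imputing an incomplete new-therapy date without regard to scan dates (SAP 6.6) can censor a PFS event when PD is scanned after the last dose

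*SAP*

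**What the plan says.** SAP 6.6 has a specific rule for this date: "For the purposes of potential PFS censoring incomplete start dates of subsequent anti-cancer therapy will be imputed". It continues: "The earliest possible date will be assumed, if this results in a start date prior to the stop date of study treatment", then "this will be defaulted to study treatment stop date + 1 day". Treatment stop is the only lower bound, and scan dates are not mentioned.

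SAP Table 5.1: 1 puts subsequent therapy above the other outcomes. Its last row covers "Subsequent anti-cancer therapy started before the outcomes flagged" with an asterisk, which include PD and death, and makes them censored. The footnote gives the trigger: "For these outcomes if initiation of subsequent anti-cancer therapy occurred prior to the outcome date". The censoring date becomes the last scan before that start, or randomisation if there is none. Protocol Table 7.5: 1 has the same principle ("Subsequent anti-cancer therapy started before progression or death") but is silent on incomplete dates.

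The protocol expects scans after treatment has stopped:
- Section 3.1: patients who stop for reasons other than progression or new therapy continue tumour follow-up.
- Appendix 10.4: after symptomatic deterioration, objective progression is to be sought even off treatment.
- Flow Chart footnote 10 (the chart in force before version 6): for patients starting new therapy without objective progression, "imaging should be performed prior to starting the new therapy if no image has been performed within the last 4 weeks". Imaging ends at progression or new therapy.

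**The concern.** Each rule is sensible alone. An early imputed start for new therapy looks cautious, and censoring at new therapy is a declared choice. Together they let an imputed date overrule a dated scan. If the true order is last dose, PD scan, new therapy, the patient has a PFS event. If the therapy date lacks its day, the imputed start can land before the scan and the event becomes a censored time at an earlier scan.

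This is not clearly a worst-case imputation for PFS, because it removes an event. It also works against the pre-therapy scan: the rationale for Global Amendment 4 says that scan was added so that a recent image would be available for PFS, and the same amendment reports more early drop-out for symptomatic progression than expected. At stake are a few events in a primary analysis of about 40.

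**Working it through.** **1. The plan's own figure.** Inputs from Protocol 7.7: 40 events, true HR 0.50, 1:1 allocation. With the normal approximation to the log HR, P(observed HR ≤ h) = Φ[(ln h − ln 0.50) × √events / 2].
- h = 0.60: Φ(0.1823 × 3.162) = Φ(0.577) = 71.8%, as stated.
- h = 0.75: Φ(0.4055 × 3.162) = Φ(1.282) = 90.0%, as stated.

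**2. The rules applied to dates** (therapy recorded by month, day missing).

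| Last dose | PD scan | Therapy recorded | Imputed start | PFS outcome |
|---|---|---|---|---|
| 1 March | 8 March | March | 1 March (not before the stop date, so the floor is not triggered) | Censored |
| 5 March | 17 March | March (truly 24 March) | 1 March, moved to 6 March | Censored at last scan before 6 March |
| before 20 March | 20 March | April | 1 April | Event stands |
| on or after the scan | any | any | scan date or later | Event stands |

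So two conditions are needed: the PD scan follows the last dose, and the recorded partial date also covers days before the scan. With a scan exactly one day after the last dose, stop + 1 equals the scan date and the event survives unless the last dose fell on the first of the month (12/365, about 3%). With the month missing as well, that one-day case rounds to 0%.

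**3. How often, given a partial date and a PD scan two or more days after the last dose.** Both rules were run over 365 scan dates in a 366-day year, with therapy starting H days after the scan.
- Day missing: a month of L days has L − H − 1 scan dates that lose the event (days 2 to L − H). The share is (366 − 12(H + 1)) / 365.
- Month also missing: the share is (365 − H) / 365.

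| H (days) | Day missing | Month also missing |
|---|---|---|
| 1 | 342/365 = 94% | 364/365 = 100% |
| 7 | 270/365 = 74% | 358/365 = 98% |
| 14 | 186/365 = 51% | 351/365 = 96% |
| 21 | 102/365 = 28% | 344/365 = 94% |
| 28 | 18/365 = 5% | 337/365 = 92% |

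**4. How many events.** The documents give neither the number of partial therapy dates nor the share of patients with PD first scanned off treatment. Assume 20% of 80 patients for the latter and 5–10% partial dates. (The 20% in Protocol 7.7 is a different quantity.)
- 80 × 0.20 × 0.05 to 0.10 = 0.8 to 1.6 patients with a partial date.
- Times 51–74% (H of 14 to 7 days): 0.8 × 0.51 = 0.4 to 1.6 × 0.74 = 1.2 events.
- Times 5–94% (H of 28 to 1 days): 0.04 to 1.5 events.

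These are upper-side figures, since they treat every such patient as having PD on independent review.

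**5. Effect on the stated probabilities** if events are lost and not replaced.

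| Events | HR ≤0.60, true 0.50 | HR ≤0.75, true 0.50 | HR ≤0.60, true 1.0 |
|---|---|---|---|
| 40 | 71.8% | 90.0% | 5.3% |
| 39 | 71.5% | 89.7% | 5.5% |
| 35 | 70.5% | 88.5% | 6.5% |

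Each lost event costs about 0.3 points in the first two columns.

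**The case against.** The usual pathway is treatment until investigator-assessed progression. There the scan precedes the stop, and the stop + 1 floor protects the event. The remaining cases need an off-treatment PD scan, an incomplete therapy date and, if only the day is missing, therapy starting in the scan's calendar month. The analysis is timed to about 40 independently assessed events (Protocol 7.3), so losses seen early could be replaced. Protocol 7.5 promises sensitivity analyses under alternative PFS rules, and SAP 6.6 has a general case-by-case rule for incomplete endpoint dates, documented before unblinding. This SAP covers only the exploratory, non-expanded scenario.

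All of this limits the size, and it stands. It does not remove the mechanism: the specific rule follows the general one in SAP 6.6, and no visible text gives a documented scan priority over an imputed date.

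A reader might go further than the documents allow:
- **That the protocol requires a scan before new therapy.** Footnote 10 says it should be done, for patients without objective progression, and only if there is no image within four weeks. It does not fix the order of last dose and scan.
- **That every off-treatment PD with a partial date is lost.** The same-month condition contradicts this.
- **That the loss falls mainly on control patients.** Nothing shows how partial dates or off-treatment scans divide between arms; such an imbalance would depend on a drug effect.
- **That no sensitivity analysis covers it.** Part of the SAP around section 7.4 is redacted, so absence cannot be asserted.

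**Conclusion.** The point holds as a minor one. SAP 6.6 and Table 5.1: 1 together can turn a true PD event into a censored time when PD is scanned after the last dose and the therapy date is incomplete. The number affected is unknown; under the assumptions shown it is probably at most about one of roughly 40 events. A count of one to two events might be inferred from the 0.8 to 1.6 patients above, but that omits the same-month condition. The cost is about 0.3 percentage points of the stated 71.8% per unreplaced event. That figure treats losses as falling at random; in a dataset this small, an individual reclassification could still move the estimated HR either way. No direction of bias is claimed. Protocol 1.4 reports that the primary analysis has been done, so the practical value now is a check of the existing data and a better rule for any re-analysis.

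**What to change.** Add to SAP 6.6: when only the day is missing and a tumour assessment falls in the recorded month, the imputed start is the latest of (a) the earliest possible date, (b) treatment stop + 1 day, and (c) the day after that assessment, but for (c) no later than the end of the recorded month. In the first two examples this gives 9 March and 18 March, and both PD events stand. By construction no day-missing case with the scan truly before therapy is then reclassified.

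When the month is also missing, do not apply this bound automatically, because a compatible scan could be months after therapy really began. Query the site and decide case by case, blinded, before lock.

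List every patient whose PFS outcome depends on an imputed therapy date, and show PFS under both imputations. If the list is empty, the point closes.

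The cost is a short SAP clause, a listing and one extra run. The downside is that a rare patient scanned after truly starting new therapy would count as an event; with imaging due to end at new therapy, this should be uncommon, and the paired analyses would show it.

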6.7 BASELINE, TIME WINDOWS AND CALCULATED VISITS

The last measurement observed prior to start of trial medication will be assigned to baseline. Note that for some trial procedures this may be the value measured on the same day trial medication was started. In these cases, where time of measurement is not recorded, it will be assumed that the measurements were taken prior to the intake of any study medication.

For measurements where not only the examination date but also time are recorded, examination time will be taken into account when defining baseline. Therefore, a measurement recorded on the same date as the first study drug administration will be considered as the baseline value, if and only if, the recording time was before or the same as the time of first study drug administration. If any of these times are missing and the date of the measurement is equal to the date of first study drug administration, then the measurement will be considered according to what was planned in the protocol, i.e. for safety laboratory data prior to first study medication. Note this rule will be relaxed for PRO data, as long as the baseline assessment of PROs is performed on or prior to the date of first study drug administration it will be considered as a valid baseline.

For tumour assessments, baseline evaluations must be performed no more than 28 days prior to start of trial medication.

Study days and visits will be labelled according to the flow chart of the CTP. In alignment with the CTP, study day will be calculated relative to the date of the first administration of study drug. The day prior to first administration of study drug will be 'Day -1' and the day of first administration of study drug will be 'Day 1'. Hence, 'Day 0' will not exist.

In order to identify whether consecutive imaging time points are missing for a patient a nominal time point [8, 16, 24 weeks and every 8 weeks thereafter up to 80 weeks, and every 12 weeks thereafter] will be assigned to each image. This will be achieved by creating time windows for each assessment as detailed in [Table 6.7: 1](#) below. If a patient does not have an image in one of the time windows when one is expected they will be considered as having 'missed an assessment' for that time-point. In case a patient has more than one assessment in one window, the assessment with the latest outcome will be used for the analysis unless progressive disease (PD) has been recorded earlier then PD will be used. Additionally, if a patient has multiple imaging dates within an assessment (e.g. a different target lesion imaging date to the non-target lesion imaging date), if the overall response is PD the earliest imaging date will be used, otherwise the latest imaging date will be used. Note for the slotting of imaging data and the derivation of time to efficacy events in general, 'Day 1' will be considered as the day of randomisation.

Table 6.7: 1 Nominal time-points and windows for imaging

Nominal time-point [Weeks]	Nominal time-point [Days]	Window [Days]
0	1	<=1
8	57	[2, 85]
16	113	[86, 141]
+8 weeks*	+56 days*	[+56 days, +56 days]*
80	561	[534, 603]
92	645	[604, 687]
+12 weeks*	+ 84 days*	[+84 days, +84 days]*

* For subsequent visits, add value to previous record in respective column

In a similar fashion to imaging time points, missed PRO assessments will be identified as detailed in Table 6.7: 2.

Table 6.7: 2 Nominal time-points and windows for PROs

Nominal time-point [Weeks]	Nominal time-point [Days]	Window [Days]
0	1	<=1 [#]
4	29	[2, 43]
8	57	[44, 71]
+4 weeks*	+28 days*	[+28 days, +28 days]*
80	561	[548, 589]
88	617	[590, 645]
+8 weeks*	+56 days*	[+56 days, +56 days]*

* For subsequent visits, add value to previous record in respective column

[#] Note any Course 1, Visit 1 data recorded prior to starting study medication will be defaulted to Day 1 even if it was after the randomisation date

Note if a patient discontinues study treatment and enters the follow-up for progression then PRO assessments will follow the imaging assessment schedule, so will either be 8-weekly or 12-weekly dependent upon whether reached Week 80 (Cycle 20) or not.

7. PLANNED ANALYSIS

In general (unless specified elsewhere), BI standards (3) will be followed for the End-Of-Text tables. In summary:

- The set of statistics for continuous data is N / Mean / Standard Deviation / minimum (Min) / lower quartile (Q1) / Median / upper quartile (Q3) / Maximum (Max). Other than the Min and Max, all statistics will be presented to one more decimal place than the raw data.
- Tabulations of frequencies for categorical data will include all possible categories and will display the number of observations in a category as well as the percentage (%) relative to the respective treatment group (unless otherwise specified, all patients in the respective patient set whether they have non-missing values or not). Percentages will be rounded to one decimal place. The category 'missing' will only be displayed if there are actually missing values.
- Time-to-event endpoints will be summarised in months [Months = (Days x 12) / 365.25] to one decimal place. Hazard ratios (HRs) and corresponding confidence intervals (CIs) will be presented to two decimal places. P-values will be presented to four decimal places.

